2.3 Long-Term Aims Beyond the Present Proposal

To use data collected to design and adequately power a larger-scale RCT assessing the efficacy of Vitamin D treatment in decreasing chronic pain in high-risk patients presenting for treatment in the aftermath of MVC and to reduce racial disparity in pain outcomes following MVC.

Study Design

3.1 General Design

[figure not shown]

Figure 1: Overall Study Design

3.2 Study Overview

Described the sequence of events in recruiting 90 patients in a multi-center randomized controlled trial. To assess a key primary outcome, we will enroll 50% white and 50% black MVC into the study. Each participant will be screened in based on a point of care Vitamin D test. This will be performed at the time of screening. Individuals with a Vitamin D level <100 ng/ml will be enrolled. Patients will be randomized 1:1 to receive a single dose of 300,000 IU of ergocalciferol versus placebo and followed for 3 months. At 3 months, patients will send a blood sample easily collected at home on a blood spot card to assess Vitamin D level 3 months following injury which is a key feasibility primary outcome.

Patients presenting to the ED within 24 hours of MVC (n=90, 45 non-Hispanic Black, and 45 non-Hispanic White) will receive a single dose of study drug prior to ED discharge (1:1 allocation 300,000 IU ergocalciferol or placebo). Prior to study drug administration, a baseline assessment will be performed (see below), and a fingerstick blood sample will be obtained to evaluate 25-hydroxyvitamin D level. Online survey follow-ups assessing primary and secondary outcomes and potential adverse events will be performed 3 weeks, 6 weeks, and 3 months after ED enrollment by study RAs using web-based REDCap™ software. Participants will also complete brief “flash-surveys” at the 2-week, 4-week, and 5-week timepoints using REDCap survey links. At 3 months, participants will also perform a fingerstick blood collection at home and mail the sample in a prepaid envelope to a lab to be processed to enable assessment of 3 month 25-hydroxyvitamin D concentration by treatment group.

3.3 Posting on clinicaltrials.gov

The study protocol will be published to clinicaltrials.gov prior to commencement of the trial. Results will be posted on clinicaltrials.gov when available.

3.4 Primary Study Endpoints

The primary endpoint of this study will examine the feasibility and efficacy of Vitamin D to improve overall MSP severity outcomes following motor vehicle collision in Blacks and Whites, as well as to reduce MSP outcome disparity between Blacks vs. Whites following MVC.

Outcome to assess feasibility: 90 patients will be enrolled, randomized into one of 2 treatment arms in a 1:1 ratio, and treated with study drug as a single-dose following motor vehicle collision with moderate to severe MSP within a 15-month period. Feasibility will also be measured by the ability to retain >80% of participants through 3-month follow-up, and achieve Vitamin D levels >20 ng/ml in 90% of treatment group at 3-month follow-up. In addition, will determine whether Vitamin D administration per protocol can raise Vitamin D concentration in treatment group >10 ng/ml above baseline. The concentration of Vitamin

D will be calculated before and after the treatment in each treatment arm to assess the response.

Outcome to assess efficacy: Efficacy of Vitamin D will be measured by difference in pain severity in treatment arms versus control arms. Pain reduction between treatment groups will be assessed using patient-reported overall MSP scores (0-10 NRS) obtained at the ED, 3-week, 6-week, and 3-month assessments. Estimates of efficacy will be obtained via repeated measures analysis using mixed effects models. Secondary Study Endpoints

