1.1 Background

Motor vehicle collisions (MVCs) are one of the most common traumatic stress exposures in the US, and the most common for which individuals seek emergency department (ED) care. More than 1 million Black Americans (Blacks) come to the ED after MVC each year, and >90% of such ED MVC patients are discharged home with a diagnosis of acute musculoskeletal pain (MSP)/strain only. More than 80% of these individuals report acute moderate or severe (mod/sev) MSP in the ED, and >50% of those with acute mod/sev MSP transition to chronic MSP. MVCs, as well as pain after MVC, disproportionately affect Blacks vs. Whites. For example, in our previous cohort studies 67% of Blacks had mod/sev MSP six months after MVC, vs. only 40% of Whites. Interventions are urgently needed that prevent chronic MSP and reduce these MSP outcome disparities.

One safe, inexpensive, widely available, and well-tolerated intervention, with exciting potential to achieve these goals, is Vitamin D (Vitamin D). Vitamin D insufficiency is much more common in Blacks than Whites. In the investigators' previous observational study, 77% (103/133) of Black MVC survivors had Vitamin D insufficiency at the time of ED evaluation. Such low Vitamin D levels are associated with increased inflammation and worse pain outcomes. Vitamin D has anti-inflammatory, neuroprotective, and analgesic properties, and Vitamin D treatment improves pain outcomes in a range of conditions. Results of a recent Vitamin D intervention study in another trauma population (burn survivors) found that Vitamin D treatment after burn

injury disproportionately improved pain outcomes in Black vs. White burn survivors (67% vs. 33% pain improvement at 6 weeks). Results from a recent analysis suggest that Vitamin D administration in the ED after MVC could prevent at least 70,000 Blacks from developing chronic post-MVC MSP annually.

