1.2 Investigational Agents

Some previous treatment trials of Vitamin D have elected to use Cholecalciferol (D3), rather than Ergocalciferol (D2), because of more favorable kinetics.¹ However, both have efficacy in raising serum concentration of 25-hydroxyvitamin D,² and only Ergocalciferol (D2) is available in an FDA-approved prescription formulation that is well-tolerated.^{3,4} In addition, a major benefit of Ergocalciferol (D2) is that a single dose can result in Vitamin D sufficient levels for many weeks/months (Table 1). The dose of Ergocalciferol that we propose, 300,000 IU, has been shown to effectively raise Vitamin D concentration by ~9 ng/ml, and to raise serum 25 hydroxyvitamin D concentration above 30 ng/ml (Vitamin D sufficient *levels*) for over 3 months⁵. The ability of our single-dose protocol to raise Vitamin D will be a primary feasibility endpoint of this pilot study.

Importantly, this dose is extremely well-tolerated: in previous trials, reports of side effects/adverse events is rare,⁶ many studies administering single, high-dose regimens report no side effects⁷⁻⁹, and the most common side effects have been mild GI complaints (e.g. nausea).⁶ Vitamin D administration has also been demonstrated to be safe, even among individuals who are already Vitamin D sufficient.¹⁰⁻¹² Based on the Code of Federal Regulation (CFR), Ergocalciferol will be exempt from an investigational new drug (IND) application.^{5,13-16}

Table 1. Studies demonstrating effectiveness of single-dose Vitamin D (Ergocalciferol, D2) to raise 25-hydroxyvitamin D levels

First author/year	Dose Used	Sample Size	Disease state	Magnitude increases of 25-OH Vitamin D @ timepoint
Martineau et al, 2007 ¹³	100,000 IU (PO)	N=192	Tuberculosis patients	↑ 13 ng/ml @ 6 weeks
Witham, et al, 2012 ¹⁴	100,000 IU (PO)	N=58	Stroke	↑ 6 ng/ml @ 8 weeks
Lanthan et al, 2003 ⁵	300,000 IU (PO)	N=243	Frail elderly	↑ 9 ng/ml @ 12 weeks
Alam, et al, 2017 ¹⁵	600,000 IU PO	N=143	Diabetic neuropathy	↑ 10 ng/ml @ 20 weeks
Cipriani et al, 2013 ¹⁶	600,000 IU PO	N=6	Healthy Volunteers	↑ 6 ng/ml @ 4 weeks

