1.4 Dose Rationale and Risk/Benefits

The dose of Ergocalciferol that we propose, 300,000 IU, has been shown to effectively raise Vitamin D concentration by ~9 ng/ml, and to raise serum 25 hydroxyvitamin D concentration above 30 ng/ml (Vitamin D sufficient levels) for over 3 months⁵. The ability of our single-dose protocol to raise Vitamin D will be a primary feasibility endpoint of this pilot study. Importantly, this dose is extremely well-tolerated: in previous trials, reports of side effects/adverse events is rare,⁶ many studies administering single, high-dose regimens report no side effects⁷⁻⁹, and the most common side effects have been mild GI complaints (e.g. nausea).⁶ Vitamin D administration has also been demonstrated to be safe, even among individuals who are already Vitamin D sufficient. ¹⁰⁻¹² Based on the Code of Federal Regulation (CFR), Ergocalciferol will be exempt from an investigational new drug (IND) application.^{5,13-16}

Chronic pain is associated with reduced mental and physical health and interferes with essential activities of daily life. Currently there are limited treatment options to address chronic pain once it has become established and the overarching aim of this clinical trial is to prevent chronic pain development, therefore there is a critical unmet need of safe, non-addictive, non-invasive preventative treatment options that can be administered to MVC survivors in the aftermath of an injury. This study has the potential to benefit participants and future MVC survivors and improve pain and general health outcomes. The risks of taking Vitamin D are small. Side effects from Vitamin D are rare, however, it is possible that over supplementation of Vitamin D may be associated with headache, loss of appetite, dry mouth, metallic taste, and nausea/vomiting.

The risks to the subjects in experiencing these side effects are balanced against the potential for a new, safe, non-opioid preventative treatment option for chronic pain following MVC.

Study Objectives

2.1 Primary Objective:

1. Assess the feasibility of the RCT protocol by (a) calculating recruitment rate and participant retention, and (b) measuring the ability of Vitamin D administration to generate sustained increases in whole-blood Vitamin D concentrations (assessed 3 months after MVC).

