3.6 Inclusion Criteria

1. ≥ 18 years and ≤ 65 years of age
2. Admitted to ED within 24 hours of motor vehicle collision
3. Plan to discharge to home from the emergency department
4. Stated willingness to comply with all study procedures and availability for the duration of the study (with the exception of the blood draw sample collected in the ED, which is optional)
5. Has a smartphone with continuous service ≥ 1 year
6. Able to speak and read English
7. Alert and oriented, and capable of engaging in informed consent
8. Willing to take on-time dose of study medication (2 capsules of Vitamin D or placebo)
9. Non-Hispanic white or non-Hispanic black
10. Point of care Vitamin D level <100 ng/ml
11. During ED admission pain severity must be at least 4/10 or higher

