6.1 Outcome definitions/Analysis plan/Power calculation

Assess the feasibility of the RCT protocol by (a) calculating recruitment rate and participant retention, and (b) measuring the ability of Vitamin D administration to generate sustained increases in whole-blood Vitamin D concentrations (assessed 3 months after MVC).

Outcome definitions for Feasibility will be determined by the ability of the study team to: recruit 90 patients into the trial over the 15-month recruitment period, retain >80% of participants through 3-month follow-up, and achieve Vitamin D levels >20 ng/ml in 90% of treatment group at 3-month follow-up. In addition, will determine whether Vitamin D

administration per protocol can raise Vitamin D concentration in treatment group > 10ng/ml above baseline.

Analyses: Feasibility analyses will be performed using descriptive statistics. To assess Vitamin D increase according to treatment group, paired t-test will be used.

Power: Based on our previous Vitamin D trial and other work,⁴⁰⁻⁴⁵ we estimate that observed follow-up will be ~80%. With n=90 sample, this will permit follow-up rates estimates at 3 months with 95% CI $\pm 8.3\%$. This will permit assessment of follow-up feasibility and necessary sample size for an R01 RCT, if pilot results warrant. In addition, based on our previous Vitamin D trial, assuming 80% retention and Vitamin D concentration standard deviation of 4ng/ml, we will have >99% power to detect a change of 10 ng/ml in Vitamin D level in the treatment group.

Assess **preliminary efficacy** of Vitamin D administration per protocol to (a) decrease overall MSP severity during the 3 months following MVC, and (b) reduce MSP outcome disparity between Blacks vs. Whites following MVC.

Outcome Definitions for Pain Reduction between treatment groups will be assessed using patient-reported overall MSP scores (0-10 NRS) obtained at the ED, 3-week, 6-week, and 3-month assessments. NRS scores are valid measures of pain assessment.^{46,47}

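### The 3-month target of 90% of the treated arm above 20 ng/ml is not specific to the dose: it ignores baseline level and does not use the placebo arm

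*Combined protocol and SAP*

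**What the plan says.** Section 2.1 gives one part of the first primary objective as "measuring the ability of Vitamin D administration to generate sustained increases in whole-blood Vitamin D concentrations", assessed 3 months after the collision. Sections 3.4 and 6.1 turn this into two vitamin D criteria.

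- **Level.** The trial should "achieve Vitamin D levels >20 ng/ml in 90% of treatment group at 3-month follow-up". No baseline condition and no placebo comparison is attached.
- **Change.** The next sentence asks whether the dose "can raise Vitamin D concentration in treatment group >10 ng/ml above baseline". Section 3.4 adds that the concentration of Vitamin "D will be calculated before and after the treatment in each treatment arm to assess the response". Section 6.1 states: "To assess Vitamin D increase according to treatment group, paired t-test will be used". Other feasibility results are descriptive.

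Entry does not select for a low level. Section 3.6 asks for "Point of care Vitamin D level <100 ng/ml", and section 3.2 repeats it.

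On baseline status, section 1.1 reports that "77% (103/133) of Black MVC survivors had Vitamin D insufficiency at the time of ED evaluation" in an earlier cohort. It gives no cut-off for insufficiency and no figure for White survivors, saying only that insufficiency is much less common among them. Section 1.2 says this dose has been shown to "raise serum 25 hydroxyvitamin D concentration above 30 ng/ml" and labels that level sufficient.

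**The concern.** The objective is about increases, but the level criterion scores only where treated participants end up. Someone who enters at 25 ng/ml and is still at 25 ng/ml after 3 months is a success, although the dose has changed nothing measurable. The more participants start above 20 ng/ml, the less the remainder must respond for the arm to reach 90%.

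The trial has a randomized placebo arm with levels measured at both times, yet neither criterion contrasts the arms. The pilot is meant to inform a larger trial (sections 2.3 and 6.1). A reader of its report could take a met 90% target as evidence that the single dose works when part of the result is baseline status.

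**Working it through.** **The plan's own figures.** Section 6.1 gives a follow-up precision of ±8.3%: 1.96 × √(0.8 × 0.2/90) = 8.26%, which agrees. It gives more than 99% power for a 10 ng/ml change, with 80% retention and SD 4. With 45 treated and 36 evaluable, 10/(4/√36) = 15 standard errors, so power is about 100% (two-sided 0.05 assumed). It is still about 100% if SD 4 refers to single measurements, so that the SD of change is 4√2 = 5.66. Both figures reproduce. The 90% target has no stated derivation.

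**Step 1: dilution.** Let s be the share of the treated arm that starts and stays above 20 ng/ml. The success rate needed among the rest is (0.90 − s)/(1 − s).

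| s | Needed among the rest |
|---|---|
| 50% | 0.40/0.50 = 80% |
| 61.3% | 0.287/0.387 = 74% |
| 70% | 0.20/0.30 = 67% |
| 80% | 0.10/0.20 = 50% |
| 90% | 0 |

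**Step 2: what the documents say about s.** The insufficiency figure is 103/133 = 77.4%, and half the sample is Black (section 3.2).

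- *If insufficiency means 20 ng/ml or below*, at most 22.6% of Black participants start above 20. Even with every White participant above 20, s is at most 0.5 × 0.226 + 0.5 × 1 = 61.3%.
- *If it means below 30 ng/ml*, s depends on f, the unstated share of insufficient Black participants who lie between 20 and 30. The Black share above 20 is then 0.226 + 0.774f. For s = 90% with every White participant above 20, that share must be 80%, so f = (0.80 − 0.226)/0.774 = 74%.

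**Step 3: chance of passing with no dose effect.** Assume each participant stays on the same side of 20 ng/ml as at baseline. With 36 evaluable, 0.90 × 36 = 32.4, so at least 33 successes are needed. The chance is P(X ≥ 33) for X binomial(36, s).

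| s | Chance of passing |
|---|---|
| 50% | <0.0001 |
| 61% | <0.0001 |
| 70% | 0.002 |
| 80% | 0.05 |
| 85% | 0.19 |
| 90% | 0.51 |
| 95% | 0.90 |

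If all 45 treated participants return a sample (41 needed), the chance is 0.04 at 80% and 0.53 at 90%.

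Under the 30 ng/ml reading, take 18 Black and 18 White evaluable participants and assume 80% to 100% of the White participants start above 20. The chance runs from 0.002 to 0.04 at f = 50%, from 0.06 to 0.53 at f = 75%, and from 0.24 to 0.95 at f = 90%. These f values are assumptions; the documents give none.

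**The case against.** The best defence is the companion criterion. A participant who starts at 25 and stays there adds nothing to a mean rise above 10 ng/ml, and that criterion has its own test and power statement. The two can be read as complementary: one asks whether treated patients end at an adequate level, the other whether the dose moved them. This stands, and a reader who infers that nothing in the plan measures change would be wrong. It does not settle the point. The paired t-test is within arm, no between-arm contrast is specified, and the plan does not say whether one or both criteria must be met. That matters because sections 1.2 and 1.4 expect a rise of about 9 ng/ml at this dose, so the level target could be met and the change target missed.

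A reader might also infer that the level target is likely to be met with no dose effect at all. The documents do not support that. If the cut-off for insufficiency is 20, the chance is below 0.0001. If it is 30, the risk is real only when about 80% or more of the arm starts above 20.

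Nor do the documents make the 90% figure a formal go/no-go rule. Section 6.1 calls the feasibility analyses descriptive and mentions a larger trial only if pilot results warrant it.

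Section 2.2 plans stratified analyses by initial level and exploratory analyses restricted to deficient participants, and section 3.2 says the 3-month level will be assessed by group. These help, but neither is tied to this criterion.

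**Conclusion.** The level criterion is not specific to the dose. It credits baseline status, so on its own it cannot show the sustained increase that the objective names. On the documents' own figures, and if insufficiency means 20 ng/ml or below, the dilution is moderate: at the 61% bound, about 74% of the remaining participants must still respond. If the cut-off is 30 ng/ml, dilution could be much greater, with a no-effect pass chance of about 5% at s = 80% and about 50% at s = 90%.

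This rests on five assumptions: the 77% from the earlier cohort carries over to the Black half of this trial; the races are balanced within the treated arm; the denominator is participants with a 3-month level; 90% means at least 90%; and levels do not drift with season or measurement.

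It is a defect of reporting and interpretation that can be repaired with data the trial already plans to collect.

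**What to change.** Leave entry and the all-treated 90% figure as they are. In sections 3.4 and 6.1:

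1. Report the proportion above 20 ng/ml at 3 months in both arms, with the between-arm difference and 95% CI.
2. Report the same proportions split by baseline level, at or below 20 against above 20 ng/ml. Do not move the 90% target to the low-baseline group. At the 61% bound it would hold only about 14 of 36 evaluable treated participants (36 × 0.387 = 13.9), and selecting on a low reading invites regression to the mean.
3. Compare change from baseline between arms, for example with baseline adjustment, beside the within-arm paired t-test.
4. State that the conclusion that the dose raises levels rests on the change and between-arm results, not on the level criterion alone.

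Both arms already give a baseline and a 3-month sample, so no new data are needed. The cost is some SAP wording, a little more analysis, and wide intervals in the low-baseline group.

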3.5 Primary Safety Endpoints

To assess safety, adverse events will be tracked using REDCap through emailed/text-messaged surveys during the drug treatment to assess side effects and safety profile of Vitamin D. Qualitative analysis of adverse events will be performed by investigative team.

3.6 Inclusion Criteria

1. ≥ 18 years and ≤ 65 years of age
2. Admitted to ED within 24 hours of motor vehicle collision
3. Plan to discharge to home from the emergency department
4. Stated willingness to comply with all study procedures and availability for the duration of the study (with the exception of the blood draw sample collected in the ED, which is optional)
5. Has a smartphone with continuous service ≥ 1 year
6. Able to speak and read English
7. Alert and oriented, and capable of engaging in informed consent
8. Willing to take on-time dose of study medication (2 capsules of Vitamin D or placebo)
9. Non-Hispanic white or non-Hispanic black
10. Point of care Vitamin D level <100 ng/ml
11. During ED admission pain severity must be at least 4/10 or higher

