3.7 Exclusion Criteria

1. Substantial comorbid injury (e.g., long bone fracture)
2. Pregnancy/breastfeeding
3. Prisoner status
4. Chronic daily opioid use prior to MVC (>20 mg oral daily morphine equivalents)
5. Active psychosis, suicidal ideation, or homicidal ideation
6. Plans for hospital admission
7. Known chronic kidney disease, stage 4 or higher ($GFR \leq 29$)
8. Intubated and sedated at time of enrollment
9. Inability to provide informed consent (receipt of sedative, hypnotic agent making the patient non-decisional for consent)
10. Known hypercalcemia
11. Vitamin D supplements in excess of 800 IU daily

12. Any other history or condition that would, in the site investigator's judgement, indicate that the patient would very likely be non-compliant with the study or unsuitable for the study (e.g., might interfere with the study, confound interpretation, or endanger patient)

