5.1 Enrollment Procedures

This first visit will take place upon admission to the hospital following MVC within 24 hours of the collision. Patients who meet inclusion criteria/exclusion criteria based on a review of the electronic medical record by research assistants, participants will be approached for participation. If the patient is interested in participating, they will then undergo informed consent. At this point in time, the participants will undergo baseline assessments (administered through REDCap) and collections of point of care Vitamin D levels with blood spot card. The participants will also have the option to consent to collect additional blood during a standard of care procedure while in the ED. The study would collect an EDTA tube,

a sodium heparin tube, and PAX gene RNA and DNA tubes. Patients with a Vitamin D level <100 ng/ml, will then take the baseline questionnaire. After all baseline data is collected, participants will be randomized and then administered appropriate study medication (Vitamin D or placebo). This administration will be documented in the MAR. Patients will be given a paper copy of their consent. Upon discharge of the patient, the patient will be given supplies to perform a home fingerstick blood draw (similar to one collected in the ED for baseline) and blotting on a blood spot card, which will occur at the 3-month timepoint.

Medical record information abstracted at time of admission will include information related to patient past medical history and initial motor vehicle collision care, and medication use prior to admission and prior to enrollment. Laboratory values relevant to patient renal and hepatic function will also be recorded (if obtained) along with any toxicology labs obtained by the primary treating team.

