Demographic and phenotypic data will be collected at this time. Patients will be asked to report demographic information including age, sex, ethnicity, education level, income level, and marital status. In addition, patients will be administered an enrollment survey which will collect domains important to the pain experience. These are listed in table 2. All patient information will be recorded by a trained research assistant or the patient via direct entry. We will assess treatment expectation using a modified survey that uses Likert scales prior randomization. In addition, we will administer weekly surveys of pain severity and to assess whether adverse events are experienced weekly through 6 weeks (these brief surveys will be sent at 2 weeks, 4 weeks and 5 weeks). Adverse events will also be monitored at 3 weeks, 6 weeks, and 3 months following administration of study drug.

Table 2. Assessments by domain at each timepoint

Domain	Measure	D1	3W	6W	3M
Demographic information	Age, sex, gender, race/ethnicity, education, income, marital status	●			
Pre-MVC	Pain catastrophizing scale ²⁶ , PROMIS Item Bank v1.0 - Emotional Distress – Anxiety ²⁷ , PROMIS Item Bank v1.0 - Emotional Distress - Depression ²⁷ , Anxiety Sensitivity Index ⁵¹	●	●	●	●
Traumatic Event	Details of Traumatic Event, Concussion, Traumatic Brain Injury, Life events checklist ²⁸	●			
MVC Injury Severity	Abbreviated injury scale ²⁹	●			
Pain	Numeric Rating Scale, [†] RPS ³⁰ , PROMIS Short Form v1.0 - Pain Interference 4a ³¹ , PROMIS Scale v2.0 - Neuropathic Pain Quality 5a ³² , PROMIS Scale v2.0-Nociceptive Pain Quality 5a	●	●	●	●
Somatic Symptoms	Pennebaker Inventory of Limbic Languidness ⁵²	●	●	●	●
Global Mental and Physical Health	PROMIS Scale v1.2 - Global Mental 2a ³³ , PROMIS Scale v1.2 - Global Physical 2a ^{33,34}	●	●	●	●

Anxiety/Depressive Symptoms	PROMIS Item Bank v1.0 - Emotional Distress – Anxiety ²⁷ , PROMIS Item Bank v1.0 - Emotional Distress - Depression ²⁷	●	●	●	●
Posttraumatic stress symptoms	PTSD Symptom Severity index-interview for DSM-5 ³⁵ , Peritraumatic Distress Inventory items (PDI) ⁵³	●	●	●	●
Dissociative Symptoms	Michigan Critical Events Perception Scale ³⁶	●			
Analgesic Medication Use	Daily milligram morphine equivalents, non-opioid analgesic use, Date of opioid cessation (first day in three consecutive where patient took no opioids) ³⁷ .	●	●	●	●
Substance abuse	PROMIS Short Form v1.0 - Severity of Substance Use (Past 30 days) 7a ³⁸	●	●	●	●

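### The trial aims to prevent chronic pain but schedules no rating of pre-collision pain; this costs some precision and clarity of interpretation, while the randomised comparison stays valid

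*Combined protocol and SAP*

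**What the plan says.** **Aim.** Section 1.4 says that "the overarching aim of this clinical trial is to prevent chronic pain development". The Introduction adds that the pilot should supply effect size and variability for powering a larger trial.

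**Entry.** The pain criterion in section 3.6 is "During ED admission pain severity must be at least 4/10 or higher". Nothing requires the pain to be new, worse than usual or caused by the collision.

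**Exclusions (3.7).** None names chronic pain. The nearest is "Chronic daily opioid use prior to MVC (>20 mg oral daily morphine equivalents". Item 12 also lets the site investigator exclude a patient judged "unsuitable for the study (e.g., might interfere with the study, confound interpretation, or endanger patient", without mentioning pain.

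**Measurement (5.1, Table 2).** At enrolment, "patients will be administered an enrollment survey which will collect domains important to the pain experience". The Pre-MVC row holds the "Pain catastrophizing scale", two PROMIS distress banks and the Anxiety Sensitivity Index. Pain instruments, such as the "PROMIS Short Form v1.0 - Pain Interference 4a", sit in a separate row that starts on D1, after the collision. No pre-collision recall version is described.

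**Indirect sources.** Chart abstraction at admission covers "information related to patient past medical history and initial motor vehicle collision care" as well as earlier medication. Section 4.6 collects prior analgesic and anti-inflammatory treatment at enrolment.

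**Outcome and analysis.** The efficacy outcome is overall musculoskeletal pain (0-10 NRS) in the ED and at 3 weeks, 6 weeks and 3 months (3.4, 6.1). The model has treatment, race, their interaction and a random intercept. Minimisation uses race, sex and pain score (4.3). The secondary analyses in 2.2 cover sex, race, baseline vitamin D and psychosocial factors. Prior pain appears in none of these.

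**The concern.** Someone who has had back pain for years and manages it without opioids, or with a dose at or below the threshold, can enter with an ED score of 4 or more. If that person scores 5 at 3 months, the data cannot show whether this is the usual level or a new problem. In a trial motivated by prevention, and by a racial gap in pain after a collision, that distinction matters for interpretation.

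Three things are at stake:
- a covariate likely to predict follow-up pain is not available;
- a chance difference between arms in prior pain can be neither seen nor adjusted for;
- a Black-White difference in 3-month pain cannot be separated from one that existed before the collision.

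Section 6.1 plans a blinded review to settle the covariates before unblinding, but that review cannot add a score that was never collected. Asking later means longer and less reliable recall, after treatment has been given.

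**Working it through.** The plan gives no figure on prior pain. It does give the follow-up assumption used below: 80% of 90. Its stated precision reproduces: 1.96 × √(0.8 × 0.2 / 90) = 8.26%, against ±8.3% in 6.1.

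**1. Can patients with prior pain enter, and are they identifiable?** Taken together, 3.6 and 3.7 admit them unless they exceed the opioid threshold or a site uses item 12. Past history, prior medication and D1 analgesic use can flag diagnosed or treated cases. They give no intensity or duration, and no planned analysis uses them for this purpose.

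**2. Effect on the race terms.** Code race as 1 for Black and 0 for White (the coding is assumed). The model's cell means are:
- White, placebo: β0
- White, vitamin D: β0 + β1
- Black, placebo: β0 + β2
- Black, vitamin D: β0 + β1 + β2 + β3

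If pre-collision pain raises follow-up pain in Black participants by δ in both arms, both Black means rise by δ. Then β2 becomes β2 + δ and β3 is unchanged. The gap itself is affected; the test of narrowing is not. β3 moves only if prior pain modifies the response. If the effect differs by γ in those with prior pain, and their shares are q_B and q_W, then β3 contains (q_B − q_W) × γ.

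**3. Lost precision.** Let r be the correlation of pre-collision pain with a participant's follow-up pain, given the terms already in the model. Adjustment multiplies the standard error by √(1 − r²). The values of r are assumptions.
- r = 0.3: √0.91 = 0.954, a reduction of 4.6%
- r = 0.4: √0.84 = 0.917, a reduction of 8.3%

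**4. Chance imbalance.** With 45 per arm and a share q with prior pain (assumed), simple randomisation gives the difference in shares between arms a standard deviation of √(2q(1 − q)/45).
- q = 0.10: √0.0040 = 6.3 percentage points
- q = 0.20: √0.0071 = 8.4 points
- q = 0.30: √0.0093 = 9.7 points

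Minimising on ED pain score reduces this to the extent that ED pain and prior pain are related.

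**5. Dilution, only if long-standing pain does not respond at all.** The mean effect becomes (1 − q) times its size, and the sample size for equal power grows by 1/(1 − q)². For q = 0.10, 0.20 and 0.30 the growth is 1.23, 1.56 and 2.04 times. As an illustration, assume a difference of 1.5 points, SD 2.5, two-sided 0.05 and 36 per arm (80% of 45). Power is Φ(1.5(1 − q) / (2.5√(2/36)) − 1.96), which gives 72% at q = 0, then 63%, 53% and 43%. None of these inputs is in the documents.

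**6. Size of a restricted analysis.** 90 × 0.8 = 72 followed; 72/4 = 18 per race-by-arm cell. Removing 10 to 30% leaves about 16 to 13.

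**The case against.** The declared outcome is mean pain severity over 3 months, not new chronic pain, so the main comparison does not require new pain to be separated from old. Arms are randomised, and assignment is balanced on race, sex and ED pain score. That stands: the treatment contrast is not systematically biased.

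A reader might infer that the treatment effect must be diluted. The documents do not support this. Section 1.3 cites benefit in established conditions, including fibromyalgia, low back pain and osteoarthritis, so patients with long-standing pain may respond. Step 5 is conditional on their not responding.

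A reader might also infer that a racial difference in prior pain biases the test of narrowing. Step 2 shows that it enters β2, and reaches β3 only through effect modification.

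Nor is it right that prior pain could not be identified at all: item 12 of 3.7, section 4.6 and the chart abstraction give partial screening and partial flags.

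Two cautions on the remedy also stand. Recall while in acute pain is imperfect, and a gain of 5 to 8% in standard error is modest. Finally, the RPS entry in Table 2 carries a dagger whose footnote is missing from the text available for review. If it defines a pre-collision version, part of the measurement gap closes, though prior pain would still have no place in the analysis.

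**Conclusion.** The point holds as a cheap improvement that should be made; it is not an error that invalidates the comparison. The plan states a prevention aim, admits patients with earlier pain, and, as the text reads, schedules no rating of that pain.

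The cost is a standard error about 5 to 8% larger than it need be (if r is 0.3 to 0.4), a possible imbalance between arms with a standard deviation of roughly 6 to 10 percentage points that nobody could check (if q is 10 to 30%), and 3-month pain and its racial gap that cannot be read as arising after the collision. The documents give neither r nor q, so these sizes are illustrations. Any loss of effect size or power depends on the further assumption that long-standing pain does not respond.

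**What to change.** 1. Check the RPS footnote. Unless it already defines a pre-collision measure, add two items to the Pre-MVC row of Table 2, at D1 and before randomisation: a 0-10 rating of average musculoskeletal pain in the month before the collision, and a yes/no item on pain on most days for 3 months or more.
2. In 6.1, pre-specify the pre-collision score as a fixed covariate in the pain models, rather than leaving it to the blinded review.
3. Report the score by arm and by race.
4. If an analysis of patients with a pre-collision score below 4 is added, label it exploratory, because the race-by-arm cells will hold about 18 or fewer.

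Eligibility, treatment and visits stay as they are. The cost is about a minute of survey time in the existing REDCap enrolment survey, one model term and one table. The weakness is recall of the previous month by people in acute pain. Because the questions come before randomisation, that error cannot depend on the assigned arm.
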